3.1.1 Data Source(s)

Several observational data sources from different countries will be included in this study to obtain a large enough population. These databases include MarketScan and Humedica databases from the United States, the DAISY database from Sweden, the DAPHNE database from Norway, the DAFFODIL database from Denmark and from the United Kingdom the Clinical Practice Research Datalink (CPRD), The Health Improvement Network (THIN), the “Diabetes Patienten Verlaufsdokumentation” (DPV) register from Germany and Manitoba Centre for Health Policy (MCHP) in Canada. AstraZeneca has access to several of these databases in-house. The databases are described more in detail in the full protocol (D1690R00015).

The contents and coverage of different variables vary between databases, therefore a set of core variables for both patient characteristics and CV events and mortality will be developed which will be described in all databases. In addition, specific variables of interest including baseline characteristics and CV events and mortality available in a limited number of the databases will also be described where appropriate.

Based on the results from the initial study (Step 1), meta-analyses for hospitalization for heart failure and all-cause mortality are feasible when including exposure-time data from all countries. However, there may not be enough subjects and person-years of exposure in the databases for each country to do standalone analyses for either endpoint. Therefore,

the analyses for these countries will be incorporated into a meta-analysis, the details of which are described below (Section 5.1).

3.2 Study Population

New users will be defined as individuals with T2DM either receiving or filling a prescription of a SGLT-2i or other GLD during the study period. The other GLD comparator group will include all diabetes medicines, allowing combinations and monotherapy use with the exception of SGLT-2i. Comparators will be matched on baseline characteristics for up to a 1:3 ratio for each SGLT-2i user.

The class SGLT-2i include dapagliflozin, canagliflozin and empagliflozin. Individuals with a previous issued/filled prescription of that medicine class during the preceding year (i.e. 365 before the index date) are not regarded as new users.

The date of the first issued /filled prescription of the SGLT-2i and other GLD classes (index medication group) during the study period will be denoted the *index date*. For the group consisting of all other diabetes medications except SGLT-2 inhibitors the first initiation of a new diabetes medication class will be the index date for those in this group initiating only one treatment episode during the study period. For patients in this group initiating two or more diabetes medication classes during the study period, one of the episodes will be randomly selected and the first day of that episode will be the index date for that patient.

A history of CV event is defined as a diagnosis of MI, unstable angina, stroke, heart failure, TIA, coronary revascularization (CABG or PCI) or occlusive peripheral artery disease before the index date. ICD-codes for these are provided in Table 8.1 in section 8 in the full protocol (D1690R00015). Other CV risk factors that also will be assessed but not included in the definition of history of CV events include obesity, dyslipidemias (hypercholesterolemia), hypertension, end stage renal disease and low socioeconomic status. These will be assessed where possible.

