To assess the possible imbalances in baseline covariates between treatment groups which may result in confounding, a propensity score approach will be utilized. Propensity scores will be calculated after the relevant inclusion/exclusion criteria are applied. The propensity score for each subject is the predicted probability of being assigned to a particular treatment conditional on a set of observed covariates. All observed variables that may affect treatment assignment or the outcome of interest will be included in the propensity score [7]. The variables to be considered for the estimation of the propensity score include age at index date, gender, duration of lookback time, indicator variable for time from start of the study period to the index date, indicator variable for whether the index medication was an add-on or switch from the previous medication, medical conditions, cardiovascular risk factors, indicators of diabetes severity (including duration of diabetes), short or long term insulin use, other concomitant medications, lifestyle/socioeconomic status indicators, and indicators of health care utilization. Patients will be grouped into categories such that patients within a certain category should have similar propensity scores. To determine whether there is balance in key covariates between treatment groups, the covariate distribution between the treatment groups will be compared by creating a table with the frequency distribution of each key covariate by index drug use before and after propensity score matching. For matching the following method is proposed: nearest neighbor caliper width of 0.25 multiplied by the standard deviation of the propensity score distribution [7].

Descriptive analyses

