Once the propensity scoring has been applied and the matched groups of SGLT-2i and control subjects have been created, certain baseline and disease characteristics (covariates) will be described by treatment group. These baseline characteristics can include age, gender, duration of diabetes, HbA1c, geographic region of residence, medical conditions, cardiovascular risk factors, concomitant medications, and certain lifestyle/ health care utilization variables, as data permit. These lifestyle/ health care utilization variables can include body mass index, smoking history, alcohol use, socioeconomic status, race/ethnicity, number of outpatient visits, number of hospitalizations, number of emergency department visits, and number of specialty care visits. These characteristics will be assessed for all patients and for patients at high baseline CV risk, respectively.

Categorical variables will be described by frequencies and percentages. Continuous and count variables will be described using mean (\pm standard deviation [SD], 95% confidence intervals (95%CI), median (quartiles), and minimum and maximum values. The proportion of patients falling above/below certain weight/BMI and HbA1c thresholds will be derived.

The incidence of acute myocardial infarction and atrial fibrillation respectively will be estimated by country/database and by treatment group.

Comparative analyses

Incidence analyses of hospitalization for heart failure and all-cause mortality will be conducted by treatment group. Only the first episode of the event will be included in the incidence analyses (however, the subsequent events within a subject will be summarized descriptively in a separate display). Person-time at risk for each patient will be the length of the index exposure episode, defined as the number of days from the day after the index prescription start date to the last day of follow-up. For each outcome of interest, the crude incidence rate in each index exposure group is the number of incident events divided by the total number of person-years at risk and will be expressed per 100 person-years with 95% confidence intervals. The incidence rates for the SGLT-2i group and control group will then be compared using a hazard ratio and corresponding 95% confidence interval. This analysis will be performed using Cox proportional hazards regression or some other suitable method if the assumptions for the Cox model are not met.

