An as-treated approach will be used for the primary analysis to account for additions or switches to the index assigned treatment. A grace period of the duration of last issued prescription will be applied. As a sensitivity analysis, an intent-to-treat approach will also be applied in which subjects will be analyzed according to the treatment they were originally assigned to, regardless of whether there were any subsequent treatment changes. Further details regarding both these approaches, including the censoring rules, potentially allowing for time varying factors and imputation of missing data, will be provided in the SAP.

Meta-analysis

A meta-analysis approach, based on the DerSimonian and Laird method [6], will be used where the hazard ratio point estimates for each country are pooled together to obtain an overall summary weighted point estimate. In this approach, random-effects models with inverse variance weighting for each country will be implemented. Up to a 1:3 treatment allocation ratio of SGLT-2i to control patients will be applied to ensure that there are enough SGLT-2i patients for analysis.

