5.3 Sample Size and Power Calculations

Power calculations

The primary endpoint will be hospitalization for heart failure. A risk reduction in this endpoint of 20% for the SGLT-2i group compared to the control group will be considered clinically meaningful. For 85% power to detect a risk reduction of 20% with a two-sided alpha level of 0.05, and up to 1:3 treatment allocation of SGLT-2i to the comparator arm, a total of 970 events will be needed across both treatment groups and all databases after the matched SGLT-2i and control groups have been created (Table 1). This calculation assumes the background rate of hospitalization for heart failure in the standard of care group is 0.625 events per 100 person-years and assuming a 20% reduction a rate of 0.5 events per 100 person years in the SGLT-2i group. For 1:3 treatment allocation, approximately 40,842 person-years will be needed in the SGLT-2i group and 122,526 person-years will be needed in the control group. However, the key driver for the power and the analysis is the number of events. The sample size is merely an approximation of how many person-years might produce the required number of events based on the assumed event rates. Also, the ratio of SGLT-2i: control matching may vary across the databases but as long as a total of 970 events are achieved, the analysis will be sufficiently powered.

The background rate of 0.625 events per 100 person-years is relevant for US, UK and Germany based on literature and empirical rates from the databases included in the study. Based on Swedish data, a substantially higher rate of 1.58 events per 100 person years has been observed. This difference in rates could be due to the age distribution and other factors including case ascertainment and baseline cardiovascular risk.

As there may not be enough statistical power for a standalone analysis in any of the individual country databases, a meta-analysis approach will be used to conduct the treatment comparison by pooling the hazard ratio estimates from all of the databases assuming that a total of 970 events have been observed. The higher rate of 1.58 events per 100 person years may apply in Sweden and the other Nordic countries. This higher event rate allows for the possibility of a sufficiently powered analysis in the Nordics alone. If 970 events have been observed in the Nordics, then a separate analysis will be submitted

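### Matching at up to 1:3 permits a variable number of controls per SGLT-2i user within a database, but the balance table, crude rates and Cox model as specified make no allowance for it, which can leave part of the confounding in the primary hazard ratio

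*Combined protocol and SAP*

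**What the plan says.** Matching. Section 3.2: "Comparators will be matched on baseline characteristics for up to a 1:3 ratio for each SGLT-2i user". The Meta-analysis paragraph of section 5.1.1 repeats the ceiling and gives keeping enough SGLT-2i patients as the reason. The proposed method in section 5.1.1 is "nearest neighbor caliper width of 0.25 multiplied by the standard deviation of the propensity score distribution". Whether controls are drawn with replacement is not stated.

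Balance. Section 5.1.1 assesses it by "creating a table with the frequency distribution of each key covariate by index drug use before and after propensity score matching". It gives no threshold and no action if balance is poor.

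Comparison. Section 5.1.1, Comparative analyses: "the crude incidence rate in each index exposure group is the number of incident events divided by the total number of person-years at risk". The two groups are then compared by a hazard ratio: "This analysis will be performed using Cox proportional hazards regression or some other suitable method if the assumptions for the Cox model are not met". The text mentions no weights, matched-set strata, covariates or clustered variance.

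What is left to a separate SAP. The list in section 5.1.1 concerns the as-treated and intent-to-treat approaches: "Further details regarding both these approaches, including the censoring rules, potentially allowing for time varying factors and imputation of missing data". Matched-set handling is not on it. Section 2.1 also refers to the SAP for how the adequacy of the propensity-score match is judged.

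Other mentions of the ratio. Section 5.3: "the ratio of SGLT-2i: control matching may vary across the databases but as long as a total of 970 events are achieved". Section 5.2.3 speaks of the 1:3 ratio without the words 'up to', and lists as a limitation that it may make the selected SGLT-2i patients less representative.

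**The concern.** In nearest-neighbour caliper matching, how many controls a user obtains depends on the propensity score. Users in regions with many comparators get three, and users with a high propensity for SGLT-2i may get one or two. Each set is balanced internally, but when the sets are pooled, the easily matched users are represented three times among the controls and the others once or twice. The pooled arms then differ in the very covariates that were matched.

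If those covariates predict heart-failure hospitalization, an unweighted hazard ratio is confounded. Section 5.2.1 names propensity-score matching as the remedy for channeling and names no other. Sparse regions are plausible from the plan's own text. Section 1.1 says SGLT-2i were recommended mainly as third-line treatment and that users probably differ. Section 5.1.1 puts calendar time and add-on/switch status in the score. Section 5.2.3 expects comparators to have earlier index dates.

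**Working it through.** **The plan's own figure.** Inputs from section 5.3: "For 85% power to detect a risk reduction of 20% with a two-sided alpha level of 0.05", 1:3 allocation, 970 events. Schoenfeld: events = (1.960 + 1.036)² / [0.25 × 0.75 × (ln 0.80)²] = 962, against 970 stated; power at 970 is 85.3%. Person-years: 970 / (0.005 + 3 × 0.00625) = 40,842 for SGLT-2i, and three times that, 122,526, for controls. Both reproduce. If the achieved ratio falls below 1:3, power at 970 events rises (90.6% at 1:2, 93.5% at 1:1). The issue is therefore bias, not power.

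**Form of the bias.** Let matched user i have baseline rate rᵢ and kᵢ controls with that same rate, and let the true ratio be 1. The SGLT-2i rate is mean(r). The unweighted control rate is Σkᵢrᵢ/Σkᵢ. Hence

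unweighted ratio = mean(r) × mean(k) / mean(kr) = 1 / [1 + cov(k, r) / (mean(k) × mean(r))].

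The bias is zero if k is constant or unrelated to risk. It falls below 1 if users with few controls are at lower risk, and above 1 if they are at higher risk. With weights 1/kᵢ the control rate is mean(r) and the ratio is 1.

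**Two strata (assumed inputs).** A share q of users get one control and have relative risk ρ; the rest get three and have risk 1. Ratio = [qρ + (1−q)] / {[qρ + 3(1−q)] / [q + 3(1−q)]}. For q = 0.5, ρ = 0.5: 0.75 / (1.75/2) = 0.857.

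| q | ρ = 0.5 | ρ = 2 |
|---|---|---|
| 0.10 | 0.967 | 1.062 |
| 0.25 | 0.921 | 1.136 |
| 0.50 | 0.857 | 1.200 |

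The last row is severe: half of the users have a single control, and risk differs twofold.

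**Simulation (assumed inputs).** 20,000 initiators; one standard normal confounder with slope 0.8 in the logistic propensity model; log-rate slope −0.4 or +0.4; true ratio 1; nearest neighbour without replacement; caliper 0.25 SD of the score; up to three controls. The rate ratio stands in for the Cox hazard ratio. SMD is the standardised mean difference.

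| SGLT-2i share | Matched users with 3 controls | Slope | Unmatched | Matched, unweighted | Matched, 1/k weights | SMD, unweighted |
|---|---|---|---|---|---|---|
| 6% | 97% | −0.4 | 0.752 | 0.992 | 1.000 | 0.030 |
| 6% | 98% | +0.4 | 1.368 | 1.010 | 1.000 | 0.017 |
| 14% | 77% | −0.4 | 0.736 | 0.952 | 0.999 | 0.156 |
| 14% | 79% | +0.4 | 1.346 | 1.071 | 1.001 | 0.148 |
| 23% | 53% | −0.4 | 0.747 | 0.910 | 0.998 | 0.280 |
| 22% | 54% | +0.4 | 1.348 | 1.119 | 1.003 | 0.270 |
| 29% | 38% | −0.4 | 0.747 | 0.888 | 0.997 | 0.337 |
| 29% | 38% | +0.4 | 1.325 | 1.142 | 1.005 | 0.337 |

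Overlap matters as well as prevalence. With propensity slope 0.4 and 20-21% SGLT-2i, 83-84% of users get three controls, and the unweighted ratio is 0.971 or 1.055. A stronger confounder makes the bias larger: in a further run (40,000 initiators, 26% SGLT-2i, 47% with three controls), log-rate slopes of −0.4 and −0.7 gave 0.900 and 0.845. Fixed 1:3 sets, unweighted, gave 0.996 to 1.005.

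**Scale.** ln 0.910 = −0.094, against a planned effect of ln 0.80 = −0.223, so that bias is 0.094/0.223 = 42% of the planned log effect. The standard error at 970 events and 1:3 is 1/√(970 × 0.25 × 0.75) = 0.074, before any between-database variance, so the bias is about 1.3 standard errors. For 0.992, ln = −0.008, or about 4% of the planned log effect.

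**The case against.** Four stronger readings are tempting, and the documents do not support them.

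*That the Cox model and balance table are definitely unweighted.* Only the crude rate is unweighted by its definition. For the other two this is inferred from silence, and a separate SAP that is not available here may say more. This stands as a limit on the claim. But matched-set handling is not among the topics that section 5.1.1 defers, and the reference to the SAP in section 2.1 concerns how the match is judged, not how matched sets enter the model.

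*That matching fails to remove confounding.* It removes most of it. In the rows where about half of users get three controls, the share removed on the log scale is 1 − ln 0.910/ln 0.747 = 68%, and 1 − ln 1.119/ln 1.348 = 62%. Where nearly all users get three, the residue is negligible.

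*That the bias favours SGLT-2i.* The sign follows the confounder, as the paired rows show. Third-line use could mean more advanced disease as easily as another profile, and the documents do not settle it.

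*That a ratio varying across databases is itself harmful.* It is not: sections 5.1 and 5.1.1 analyse the countries separately and then pool the estimates. The difficulty arises only within a unit that is analysed as one.

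There is also a case that the ratio is fixed in practice. The limitation in section 5.2.3 makes most sense if users without three controls are dropped, and in that case the problem disappears. Against this, sections 3.2 and 5.1.1 both set a ceiling, and the stated aim of keeping enough SGLT-2i patients points to retaining users with fewer controls. The text supports both readings, and section 6.1.1 spreads the analyses over several organisations that could choose differently.

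Finally, an unweighted balance table would expose the imbalance rather than hide it. That is fair, but no threshold or action is attached to it. Section 5.1.1 also groups patients into propensity-score categories, without saying how these are used.

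**Conclusion.** The concern holds in a limited form. The plan permits a variable number of controls per SGLT-2i user within a database, and the analysis as written includes nothing to account for it. Followed literally, it can leave part of the confounding in the primary hazard ratio, and in the mortality comparison, which uses similar methods.

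Under the simulated inputs the null ratio is off by roughly 10-15% when about half of users obtain three controls, and by about 1% or less when nearly all do. These sizes rest on one assumed confounder, matching without replacement, and a rate ratio in place of the hazard ratio. The documents do not give the SGLT-2i share of initiators, the overlap of the scores or the strength of confounding, so the actual size and direction in this study cannot be stated. The mechanism and the remedy do not depend on those inputs.

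**What to change.** Reconcile the 'up to' wording in sections 3.2 and 5.1.1 with section 5.2.3, and state for every database one of the following:

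- **Fixed ratio within the database.** It may differ between databases. Cost: SGLT-2i users who cannot reach the ratio are dropped, or, with a lower ratio, surplus controls are.
- **Variable ratio with weights.** Weight each control by 1/(number of controls in its matched set), use a robust variance clustered on matched set, and apply the same weights to the balance table and incidence rates. Cost: one weight variable and a slightly larger standard error.
- **Cox model stratified by matched set**, as an acceptable alternative. Stratifying the model does not correct the pooled balance table or rates, so these still need the weights.

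In each case report how many users obtained one, two and three controls, by database. That shows directly whether the issue is material.

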3.3 Inclusion Criteria

Inclusion criteria are:

- New user receiving or dispensed prescription of SGLT-2i medication or other GLD, oral as well as injectable, including fixed-dose combination (FDC) products containing these medication groups
- T2DM diagnosis on or prior to the index date defined by ICD9 codes 250.X0, 250.X2 or ICD10 codes E11 and O24.1. Read codes for T2DM are presented in the full protocol (D1690R00015) Table 8.2 in section 8.
- ≥ 18 years old at index date
- > 1 year data history in the database prior to the index date

3.4 Exclusion Criteria

Exclusion criteria are:

- Patients with a T1DM diagnosis (ICD9 codes 250.x1, 250.X3 or ICD 10 codes E10 and O24.0, read codes for T1DM are presented in the full protocol (D1690R00015) Table 8.2) at any time

- Patients with gestational diabetes (ICD9 codes 648.8; ICD10: O24.4; read codes L180811 and L180900) within 1 year before index date

3.5 Participant Follow-up

Participants will be followed from the index date (excluding) until end of use of the index treatment or migration/leaving the practice/leaving the database, last date of data collection, death date (Sweden, Denmark, Norway, UK) or date of outcome.

4. VARIABLES AND EPIDEMIOLOGICAL MEASUREMENTS

4.1 Exposures

The exposure of interest is use of SGLT-2 inhibitors (dapagliflozin, canagliflozin and empagliflozin) or other GFLD including all diabetes medications except initiation of SGLT-2 inhibitors. An individual will be defined as a user on the index therapy for the duration of subsequent prescriptions. A 100 % of previous number of days' supply will be added after the last day of supply. If there is no refill within this period the patient is censored at the last day of the grace period. An individual will only be included if he or she is a new user of one of the mentioned medicine groups. Insulin use in the three months preceding index date will be assessed and descriptions of characteristics will be conducted by insulin use before index date.

An individual will be considered exposed to the medication of interest from the index date and until the last day with medication available (either last day of the last filled prescription (Sweden, Norway, Denmark, Germany, Humedica, MarketScan, Canada's MCHP) or last day of the last issued prescription (CPRD and THIN) plus a grace period of the number of day's supply contained in the last filled or issued prescription.

The SGLT-2i class is defined as the medications dapagliflozin (ATC code A10BX09, A10BD15), canagliflozin (A10BX11, A10BD16) and empagliflozin (A10BX12, A10BD19). DPP-4i includes all available medicines in the ATC category A10BH and the substances A10BD07,08,10,11,13,18 (combinations with metformin). The group other diabetes medications include all diabetes medications in A10A and A10B except SGLT-2 inhibitors. Brand names used in the US of the medication groups are outlined in Table 8.3 in section 8 appendix in the full protocol (D1690R00015).

